### **statistical analysis plan**

The comparison of results between the two groups was made with the use of an independent-sample t-test for continuous variables and contingency table analysis for categorical variables. A P value of  $<.05$  was considered to be significant. All statistical tests were two sided. Statistical analysis was performed with the use of SPSS for PC version 21(2016).

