**NCT 02648698**

**Date: May 30, 2020**

## study protocol

### Background

Chronic endometritis (CE) is a condition characterized by the presence of plasma cell in the endometrial stroma. CE may be associated with abnormal uterine bleeding, intrauterine pathology such as polyp or fibroid, as well as a variety of reproductive failure including infertility, recurrent implantation failure and recurrent pregnancy loss. In women with reproductive failure, the reported prevalence of CE maybe as high as 41%.

CE is often treated with antibiotics on the assumption that it is caused by an underlying infection. The response of CE to antibiotic therapy has been examined in a number of cohort studies. The cure rate, as determined by reduction of plasma cell density in a repeat endometrial biopsy specimen following antibiotic therapy was found to be 75.4%, 99% and 100%.

The impact of antibiotic therapy on clinical outcome among subjects with CE had also been examined in several cohort studies. Cicinelli et al conducted a retrospective study which showed that after antibiotic therapy, the pregnancy rate (PR) and live birth rate (LBR) in women who become CE negative was higher than those who remained CE positive after antibiotic treatment (65.2% versus 33.0% ; 60.8% versus 13.3%, respectively) . In another study involving women with recurrent implantation failure (RIF) study, Kitaya et al. reported that the LBR in the first embryo transform (ET) cycle and cumulative three ET cycles in the cured CE group following antibiotic treatment (32.8% and 38.8%, respectively) was significantly higher than those of the non-CE group (22.1% and 27.9%, respectively). McQueen et al observed that the cumulative LBR was 88% (21/24) for the treated CE group versus 74% (180/244) for the group without CE. In the CE group, the LBR for those before treatment was 7% (7/98) versus 56% (28/50) after treatment.

Despite the apparently encouraging clinical data from the above observational, cohort studies suggesting that antibiotic treatment was effective in curing CE and

improving the reproductive outcome, the impact of antibiotic therapy has not yet been formally examined in any randomized control trial.

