### **Objective**

To compare the cure rate of chronic endometritis between subjects who did and did not receive antibiotic treatment.

[figure not shown]

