### **Design**

Prospective, Single-blind randomized, controlled trial.

This RCT was conducted in the Hysteroscopic Centre, Fuxing Hospital, Capital Medical University, a national training centre for hysteroscopy in China between 2016 and 2018. During the period of study, women who were referred to the center for hysteroscopy for investigation of reproductive failure including infertility, recurrent miscarriage (RM) or recurrent implantation failure (RIF), as well as abnormal menstruation had endometrial biopsy obtained for histological examination including CD138 immunohistochemical staining as a routine procedure.

The inclusion criteria for patient participation in this study included: (1) CD138 immunohistochemical staining of endometrial specimen showed presence of one or more plasma cells per 10HPF which confirmed chronic endometritis, according to published criteria; (2) women who were pre-menopausal; (3) no evidence of endometrial hyperplasia or malignancy or structural uterine pathology; (4) agreement to have a second endometrial biopsy ~4 weeks after the initial endometrial biopsy; and (5) written informed consent obtained.

The exclusion criteria included: (1) women who received steroid hormone therapy within one month of recruitment; (2) allergy or suspected allergy to the chosen antibiotic therapy; (3) women who developed any concurrent infection and received any antibiotic therapy during the period of study other than the one prescribed according to the study protocol.

A total of 120 subjects were randomized in antibiotic group and control group in a 1:1 ratio using a computer-generated randomization list, 6 subjects did not attend for second hysteroscopy and endometrial biopsy. At the end, 59 subjects in the antibiotic group and 55 subjects in the control group completed the study according to the protocol, these 114 cases were included in the final analysis.

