**Methods**

Women randomized to antibiotic group received oral Levofloxacin 500 mg and Tinidazole 1000 mg daily for 14 days. Women randomized to the control group did not receive any treatment. Initially it was planned for women in the control group to take placebo, but the organization was difficult, so it was changed prior to the start of

the study to an open label study. A repeat endometrial biopsy was performed 4-8 weeks after the initial biopsy to determine if CE was still present.

The conversion rate of CE (from positive to negative) in two group were compared.

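### Does the SAP need a named effect estimate and confidence interval for conversion, beyond a contingency-table test at P<.05?

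*Combined protocol and SAP*

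**What the plan says.** The Objective is "To compare the cure rate of chronic endometritis between subjects who did and did not receive antibiotic treatment". The Methods section makes the outcome binary, read at the repeat biopsy: "The conversion rate of CE (from positive to negative) in two group were compared". The statistical analysis plan is one short paragraph. It assigns a t-test to continuous variables and "contingency table analysis for categorical variables", adds "A P value of $<.05$ was considered to be significant" and "All statistical tests were two sided", and names the software. Conversion is not mentioned by name there, but as a yes/no outcome it can only fall under the contingency-table clause.

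The Design section supplies the denominators: "At the end, 59 subjects in the antibiotic group and 55 subjects in the control group completed the study according to the protocol". Neither document part mentions a risk difference, risk ratio, odds ratio, confidence interval, specific contingency-table test or covariate. The paragraph reads as complete, so redaction or text extraction does not explain the omission.

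**The concern.** A significant test says that two cure rates differ. It does not say by how much, or how precisely the difference is known. The Background section says that antibiotic treatment had not been tested in a randomised trial, so the size of the difference from an untreated group is the main new information here. With fewer than 60 women per arm, that size would be known only to within about 14 to 17 points either way over plausible control rates. A non-significant result could also be misread as no effect when a large benefit was still possible.

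A second worry is that contingency-table analysis covers several tests (uncorrected chi-square, continuity-corrected chi-square, Fisher's exact). Near the 5% boundary they can disagree, which would leave the verdict to an unstated choice.

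**Working it through.** The plan gives no effect size, control rate or power figure, so it has no figure of its own to reproduce. The head count agrees: 120 − 6 = 114 = 59 + 55.

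**Inputs.** Analysed numbers 59 and 55 (Design). Two-sided 5% level (SAP). The conversion counts are assumptions. For antibiotic I take 44/59 = 74.6%, the whole number nearest the lowest of the three cohort cure rates in the Background (0.754 × 59 = 44.5, and 44/59 is closer to 75.4% than 45/59 = 76.3%). That cohort rate measured a different thing, namely "reduction of plasma cell density in a repeat endometrial biopsy specimen following antibiotic therapy was found to be 75.4%, 99% and 100"%, not conversion to negative. The documents give no control rate, so I vary it.

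**Step 1: what the interval would add.** The Newcombe interval combines the Wilson limits (l, u) of each arm. With d = p1 − p2:

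- lower = d − √[(p1 − l1)² + (u2 − p2)²]
- upper = d + √[(u1 − p1)² + (p2 − l2)²]

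For 44/59 v 31/55 the Wilson limits are 62.20 to 83.94 and 43.27 to 68.63 (in points), and d = 74.58 − 56.36 = 18.2.

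- lower = 18.21 − √(12.38² + 12.27²) = 18.21 − 17.43 = 0.8
- upper = 18.21 + √(9.36² + 13.09²) = 18.21 + 16.09 = 34.3

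The same formula for other control counts, with the uncorrected chi-square P value:

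| Control converting | Difference (points) | 95% CI | P |
|---|---|---|---|
| 0/55 | 74.6 | 60.6 to 83.9 | <0.001 |
| 11/55 | 54.6 | 37.1 to 67.2 | 6 × 10⁻⁹ |
| 16/55 | 45.5 | 27.5 to 59.4 | 1 × 10⁻⁶ |
| 28/55 | 23.7 | 5.9 to 39.6 | 0.009 |
| 31/55 | 18.2 | 0.8 to 34.3 | 0.041 |
| 33/55 | 14.6 | −2.6 to 30.8 | 0.097 |

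Every control count from 0 to 31 is significant, which makes 32 possible results. In 6 of them the lower limit is below 10 points.

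**Step 2: can a reader obtain this from the plan as written?** The plan compares two rates with known denominators. One woman is 100/59 = 1.7 points in one arm and 100/55 = 1.8 points in the other. Even a percentage rounded to a whole number therefore fixes the count: 75% of 59 is 44.25, so 44; 56% of 55 is 30.8, so 31. All four cells follow, and every figure in the table with them.

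**Step 3: how often the unnamed test matters.** For the cells 44, 15 and 31, 24:

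- Uncorrected: 114 × (44×24 − 15×31)² / (59×55×75×39) = 114 × 591² / 9,491,625 = 4.195, P = 0.041.
- Continuity-corrected: 591 becomes 591 − 57 = 534, giving 3.425, P = 0.064.
- Fisher's exact: P = 0.049.

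The corrected test disagrees with the other two here. At 30/55 all three are below 0.05 (0.025, 0.041, 0.031), and at 32/55 all three are above it (0.064, 0.098, 0.075). In the direction of benefit, 31/55 is the only count where the choice matters, and the difference and Newcombe interval are the same whichever test is used.

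**The case for a change.** The strongest case for a change is that two percentages are not a between-group estimate, that the plan promises no interval, and that adding one costs nothing because it uses the same four counts. The table supports this: significant results with lower limits of 60.6 and 0.8 points mean very different things, and the P value alone does not distinguish them well. That stands as good reporting advice, and a statistician writing up the trial should follow it.

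It does not establish a fault in the plan. The argument has most force if a bare P value were the only output, and the Methods section, which compares rates, does not suggest that. The 18.2-point case is a chosen scenario, resting on an assumed control rate and on a cohort rate defined differently from this trial's outcome. The risk difference with a Newcombe interval is also one sound choice among several; a risk ratio, or another valid interval, would serve equally well.

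Timing limits the gain further. The document is dated May 2020, is written largely in the past tense and reports completed numbers from a trial run in 2016 to 2018. Naming a measure or test now could not restore prespecification.

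Adjusting for the entry plasma-cell count would not strengthen the case. The Design section gives an entry threshold, "CD138 immunohistochemical staining of endometrial specimen showed presence of one or more plasma cells per 10HPF", and nothing says that a numeric count was kept. The covariate would be chosen after an open-label trial had ended. In a simulation with assumed cell densities and prognostic strengths, the median interval ranged from 0.6% wider to 10.6% narrower.

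**Conclusion.** The omission is real, but it concerns reporting detail. The planned two-sided test on a 2×2 table is a valid way to compare conversion between randomised groups, and following the plan as written yields a sound result from which the difference and its interval can be worked out. Under the assumed 44/59, the choice of test affects one control count in the direction of benefit. Leaving out an interval hides a precision of roughly 14 to 17 points either side, which any reader given the two rates can reconstruct. These sizes depend on assumed conversion counts, since the documents give none. That the information is recoverable depends only on the two denominators and on the rates being reported, as the Methods section implies. An analyst would ordinarily name the test and give an estimate with a 95% interval in the report, saying that the measure was chosen after the trial. The plan itself needs no change.
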